4.10.4 Adjustment for Multiple Hypothesis Testing

To control the Type 1 familywise rate at 5%, the serial gate-keeping approach (proposed by [Westfall and Krishen, 2001](#)) will be used to test the primary and secondary efficacy endpoints (ordered by clinical relevance and importance) during the double-blind period in the above specified sequence. It will be implemented in the following way: If (and only if) the null hypothesis associated with the primary endpoint is rejected at the 0.05 significance level, then the secondary efficacy endpoint will be tested at the 0.05 significance level. The plan for analysis of other endpoints during the double-blind period is purely exploratory, so no further adjustment is warranted. Similarly, efficacy analyses of endpoints collected during the open-label period are also exploratory, and do not warrant adjustment.

4.10.5 Safety Data Monitoring

An independent Data Monitoring Committee (DMC) will be established to review safety data periodically throughout the trial.

The DMC will operate under a charter that is approved by all committee members and the Sponsor. The scope of the review and procedures in place to maintain the integrity of the ongoing study will be described in the charter.

4.11 Safety Analysis

For the Interim Analysis, the safety analyses will cover all data collected until the database cut-off, including data from the open-label period. Safety analyses will be performed using data from the Double-Blind and Open-Label Safety Populations. Tables using the Double-Blind Safety Population will include only data collected during the

double-blind period. Tables using the Open-Label Safety Population will include only data collected during the open-label period.

In addition, select safety analyses will be performed using the Fosmetpantotenate Safety Population. Tables using the Fosmetpantotenate Safety Population will include data collected following the first exposure for fosmetpantotenate (i.e., double-blind and open-label data for patients administered fosmetpantotenate at baseline of double-blind period, open-label data only for patients first administered fosmetpantotenate at baseline of the open-label period.)

Safety of fosmetpantotenate will be determined on the basis of treatment-emergent AEs (TEAEs), vital signs, weight, physical examinations, clinical laboratory assessments, the Columbia Suicide Severity Rating Scale (C-SSRS) (in assessable patients), and ECG findings.

For the Double-Blind Safety Population, table summaries and figures will be presented by treatment group as appropriate; for the Open-Label and Fosmetpantotenate Safety Populations, safety summaries will be presented for the entire cohort, and (when indicated) by treatment received during the prior double-blind period.

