4.11.1 Adverse Events (AEs)

All AEs will be coded by Preferred Term and System Organ Class using MedDRA coding dictionary Version 20.0.

TEAEs in the double-blind period are defined as AEs that are new or are a worsening of an existing condition that begin from the day of first dose of investigational product until the day after the last dose for the double-blind treatment period. TEAEs in the open-label period are defined as AEs that are new or are a worsening of an existing condition that begin from the day of first dose of open-label investigational product. TEAEs in the fosmetpantotenate safety population are defined as AEs that are new or are a worsening of an existing condition that begin from the day of first dose of (blinded or open-label) fosmetpantotenate.

An overview of adverse events will be provided for each of the three Safety Populations that summarizes incidence in the following categories, overall, by age group (pediatric, adult), and by sex:

- Any AEs
- Any TEAEs
- TEAEs by relationship to study medication (Not related, Unlikely Related, Possibly Related or Related)
- TEAEs by severity (mild, moderate, severe)

- Any TEAEs with an outcome of death
- TESAEs
- Treatment discontinuation due to TEAEs

The incidence of TEAEs will be summarized for each treatment group by Preferred Term as well as by Preferred Term within System Organ Class. The incidence of TEAEs by severity and relationship to treatment will be summarized for each treatment group by System Organ Class and Preferred Term. A patient with several occurrences of the same AE will be counted once and classified by the most severe event (or the event with the closest relationship to study drug). If severity or causality is missing, the worst case will be assumed (i.e., “Severe” if severity is missing and “Drug Related” if causality is missing.)

In addition, the incidence of Adverse Events of Interest (AEOIs), TESAEs, TEAEs leading to treatment discontinuation, and TEAEs leading to death will be summarized for each treatment group by System Organ Class and Preferred Term.

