Incidence calculations will be based on the numbers and percentages of patients with AEs, and sorted by decreasing frequency in the fosmetpantotenate group. Although a MedDRA Preferred Term may be reported more than once for a patient, that patient will be counted only once for that MedDRA Preferred Term. For these summaries, patients with multiple AEs will be counted only once per SOC and PT. Furthermore, for each category within these summaries, the number of adverse events will be presented.

The above incidence tables will each be run using the Double-Blind, Open-Label, and Fosmetpantotenate Safety Populations.

In addition, time to event analyses (first event) will be performed for the following adverse event categories for patients in the Double-Blind Safety Population: dystonia, any AE with gastrointestinal disorder as SOC, any AEOI. Time to event endpoints will be summarized using the Kaplan-Meier method; median event times and 2-sided 95% confidence interval for each median will be provided (Brookmeyer, 1982). Time to event data will be censored using the date of a patient’s last visit during the double-blind period. The event or censoring time (days) will be calculated as:

$$\text{Date of event/censoring} - \text{Date of randomization} + I$$

Moreover, for each AE category, a log-rank test will be performed to compare time to event between the treatment groups. The Cox proportional hazard (PH) model will be fitted and the estimated hazard ratio and 2-sided 95% confidence interval will be provided. Finally, estimates of the time to event curves obtained from the Kaplan-Meier method will be presented and displayed graphically, spanning the double-blind period.

For the above three adverse event categories, the duration of each event within the event category will be summarized descriptively, for each event occurrence, for patients in the

Double-Blind Safety Population. In addition, patient-level duration of events will be displayed graphically using the MedDRA Preferred Term, spanning the double-blind period. Only patients who have had an adverse event in the given adverse event category will be presented, and multiple occurrences of a single Preferred Term will be presented on the same line.

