6.1.5 Body of the Data Display

1. Listings will be sorted for presentation in order of study phase, treatment group, as above, patient ID, collection day, and collection time.
2. For ordered categorical parameters, frequency tables will present all categories of the parameter between the minimum and maximum level, even if n=0 for all treatment groups in a given category. For example, the frequency distribution for symptom severity would appear as:

Severity Rating	n
severe	0
moderate	8
mild	3

Where percentages are presented in these tables, any counts of 0 will be presented as 0 and not as 0 (0%).

3. If the categories for a table are not ordered (e.g., Medical History, Reasons for Discontinuation from the Study, etc.), then only those categories for which there is at least 1 patient represented in 1 or more groups will be included.
4. An Unknown or Missing category will be added to the summary table of any categorical parameter for which information is not available for 1 or more patients.
5. Unless otherwise specified, the estimated mean and median for a set of values will be displayed to 1 more significant digit greater than the original values; standard deviation (SD) will be presented to 2 more significant digits than the original values. The minimum and maximum will be reported at the same number of significant digits as the original values. LSmeans will be reported to 1 decimal place, and corresponding CI's to 2 decimal places. For example, for systolic blood pressure:

n	XX
Mean	XXX.X
SD	X.XX
Median	XXX.X
Minimum	XXX
Maximum	XXX

6. Data in columns of a table will be formatted as follows:
 - alphanumeric values left-justified;
 - whole numbers (e.g., counts) right-justified; and
 - numbers containing fractional portions decimal-aligned.
7. Percentage values will be formatted with 1 digit to the right of the decimal point in parentheses, 1 space after the count (e.g., 7 (12.8%), 13 (5.4%)). Less-than signs (e.g., “<0.1%”) will appear when values are >0.0% and <0.1% (but not equal to 0.0%). Unless otherwise noted, the denominator for calculating percentages will be the number of patients in a given treatment group and analysis set.

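### AE percentages in the Fosmetpantotenate Safety Population ignore unequal time on drug, so a split by prior arm would favour ex-placebo patients for steady-hazard events even at equal risk

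*SAP*

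**What the plan says.** SAP 4.4 defines the Fosmetpantotenate Safety Population as everyone who received at least one dose of the drug in either period. SAP 4.11 fixes the data that count for it: "double-blind and open-label data for patients administered fosmetpantotenate at baseline of double-blind period, open-label data only for patients first administered fosmetpantotenate" at open-label baseline. Under SAP 4.11.1, an AE is treatment-emergent in this population if it is new or worsened and "begin from the day of first dose of (blinded or open-label) fosmetpantotenate". No end of the window is stated.

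On the measure, SAP 4.11.1 says: "Incidence calculations will be based on the numbers and percentages of patients with AEs". It adds that "for each category within these summaries, the number of adverse events will be presented", which is a count and not a rate. SAP 6.1.5 sets the default: "the denominator for calculating percentages will be the number of patients in a given treatment group and analysis set". The scope is wide: "The above incidence tables will each be run using the Double-Blind, Open-Label, and Fosmetpantotenate Safety Populations".

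On layout, SAP 4.11 says that for the Open-Label and Fosmetpantotenate populations "safety summaries will be presented for the entire cohort, and (when indicated) by treatment received during the prior double-blind period".

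Three other provisions bear on the point. SAP 4.9 summarises treatment duration from first fosmetpantotenate dose in this population. SAP 4.11.1 plans Kaplan-Meier, log-rank and Cox analyses for three AE categories, in the Double-Blind Safety Population only. The same incidence tables are also run separately on the Double-Blind and Open-Label Safety Populations. Neither document plans a patient-year, exposure-adjusted or common-window AE rate.

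**The concern.** The percentage of patients with at least one event rises with time at risk. Here the time at risk differs between the prior-arm groups by construction. Ex-active patients bring their double-blind weeks and their open-label weeks, whereas ex-placebo patients bring open-label weeks only. The interim cut-off adds a second source of variation, because open-label follow-up then depends on when a patient entered.

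Two consequences follow. If the tables are split by prior arm, part of any difference reflects length of observation and not risk. The pooled percentage, which is always shown, is an average over unlike follow-up times and has no stated time horizon. These tables go into the interim clinical study report for regulators (SAP 4.3). The raw event counts do not help, because they grow with exposure too.

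**Working it through.** The documents state no AE rate, so there is no figure of the plan's own to reproduce on this point. The check asks how large a gap the counting rule creates when the true on-drug hazard is the same in both groups.

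**Inputs from the documents**
- Double-blind period: 24 weeks (SAP 3).
- Data window by prior arm: SAP 4.11, quoted above.
- 82 randomised 1:1, so 41 per arm; 37 completers per arm targeted (SAP 3 and 4.2). Used only in the dropout variant.

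**Assumptions (mine)**
- Incidence per 24 weeks on drug, p: 10%, 20% or 30%, constant hazard, equal in both groups.
- Open-label time at cut-off, L: 12, 24, 52 or 104 weeks.

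**Formula.** h = −ln(1 − p)/24 per week and crude incidence = 1 − exp(−h·t), with t = L for ex-placebo and t = L + 24 for ex-active completers. With p = 20%, h = 0.2231/24 = 0.0093. At L = 24, ex-placebo is 1 − 0.8 = 20.0% and ex-active is 1 − 0.8² = 36.0%.

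**Crude incidence, ex-placebo vs ex-active (gap in points)**

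| L (weeks) | p = 10% | p = 20% | p = 30% |
|---|---|---|---|
| 12 | 5.1 vs 14.6 (9.5) | 10.6 vs 28.4 (17.9) | 16.3 vs 41.4 (25.1) |
| 24 | 10.0 vs 19.0 (9.0) | 20.0 vs 36.0 (16.0) | 30.0 vs 51.0 (21.0) |
| 52 | 20.4 vs 28.4 (8.0) | 38.3 vs 50.7 (12.3) | 53.8 vs 67.7 (13.9) |
| 104 | 36.7 vs 43.0 (6.3) | 62.0 vs 69.6 (7.6) | 78.7 vs 85.1 (6.4) |

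Gaps are taken before rounding. They run from 6.3 to 25.1 points.

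**Dropout.** Suppose 4 of 41 ex-active patients leave evenly over the double-blind period. At L = 24, mean exposure is (37 × 48 + 4 × 12)/41 = 44.5 weeks against 24. With p = 20%, the four have an average incidence of 1 − 0.2/0.2231 = 10.4%. The ex-active figure becomes (37 × 36.0 + 4 × 10.4)/41 = 33.5%, against 20.0%. At p = 30% and L = 104 the gap is gone: 78.7% vs 78.3%.

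**Front-loaded events.** Put 90% of the 24-week cumulative hazard H in the first 4 weeks and spread the rest evenly, at the same rate beyond week 24. With p = 20%, H = 0.2231. At L = 24 the cumulative hazards are H and 0.9H + 0.1H × 44/20 = 1.12H, which gives 20.0% vs 22.1%.

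**Does a simple rate repair it?** With a constant hazard, yes. At p = 20% both groups show 0.0093 × 52.18 × 100 = 48.5 first events per 100 patient-years. With the front-loaded hazard, no. Mean time at risk to first event or end of follow-up is 19.8 weeks (ex-placebo) and 38.7 weeks (ex-active), so the rates are 0.200/19.8 × 5218 = 53 and 0.221/38.7 × 5218 = 30 per 100 patient-years. That is a false difference in the opposite direction.

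**Does a 24-week window with crude percentages repair it?** Not at an early cut-off. If ex-placebo patients have only 12 open-label weeks and p = 20%, the figures are 10.6% vs 20.0%.

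**The case against.** The strongest reply is that these are supplementary descriptive tables with no hypothesis test. The drug-placebo comparison is made in the Double-Blind Safety Population, where both arms have the same planned 24-week window. The Open-Label tables start both groups at open-label entry. Treatment duration is reported for this population, so a careful reader can see the imbalance. The prior-arm split is conditional, since SAP 4.11 says it is made only when indicated.

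Much of this stands, and it limits the point. It does not remove it. The duration summary is never used as a denominator for AEs. The period tables align patients on study period and not on time since first active dose: in the Open-Label tables, ex-placebo patients are newly exposed while ex-active completers have already had 24 weeks. The pooled percentage is always produced.

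Two stronger readings are tempting and should not be drawn:

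- **That an observed ex-active excess would be due only to longer exposure.** The documents give no AE rates, so part of a gap could be real. The groups also differ in other ways. Ex-placebo patients begin the drug open-label with no escalation required (Protocol 6.5.2.2), whereas ex-active patients begin it blinded, with escalation (Protocol 6.5.2.1). Placebo patients who never receive the drug are not in this population.
- **That the report will set the pooled figure beside the 24-week placebo figure.** No section plans such a table. A reader of the report might make that comparison, but the plan does not.

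**Conclusion.** The point holds in limited form. The plan applies crude percentages to follow-up that is unequal by design, and no planned table aligns patients on time since first fosmetpantotenate dose. For steady-hazard events, a prior-arm split would put ex-active patients about 6 to 25 points higher at equal risk. This rests on assumed constant hazards of 10% to 30% per 24 weeks and 12 to 104 open-label weeks. The artefact is largest at an early cut-off. It is about 2 points for strongly front-loaded events and can vanish with dropout and long follow-up.

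The extra 24 weeks applies to an ex-active patient who completes the double-blind period, compared at equal open-label time. It does not describe every patient or the group mean. This is an inexpensive improvement to descriptive safety reporting and does not affect the efficacy conclusions.

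**What to change.** In SAP 4.11.1, for the Fosmetpantotenate Safety Population:

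1. Add patient-years and first-event rates per 100 patient-years with 95% confidence intervals beside the patient and event counts. Define time at risk as running from first fosmetpantotenate dose to first event, with a stated end of the at-risk window or the cut-off, whichever comes first.
2. State that rates over the whole follow-up assume a roughly constant hazard and can mislead for early-onset events.
3. Make any prior-arm split over a common window, the first 24 weeks from each patient's first fosmetpantotenate dose, censoring at the cut-off or end of follow-up. Use Kaplan-Meier cumulative incidence, or person-time within the window, and not crude percentages. Kaplan-Meier is the safer choice, because person-time rates keep the constant-hazard assumption when follow-up inside the window is unequal.

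The cost is SAP wording and slightly longer tables. The dosing and AE dates are already collected, and trial conduct does not change.

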4.11.1 Adverse Events (AEs)

All AEs will be coded by Preferred Term and System Organ Class using MedDRA coding dictionary Version 20.0.

TEAEs in the double-blind period are defined as AEs that are new or are a worsening of an existing condition that begin from the day of first dose of investigational product until the day after the last dose for the double-blind treatment period. TEAEs in the open-label period are defined as AEs that are new or are a worsening of an existing condition that begin from the day of first dose of open-label investigational product. TEAEs in the fosmetpantotenate safety population are defined as AEs that are new or are a worsening of an existing condition that begin from the day of first dose of (blinded or open-label) fosmetpantotenate.

An overview of adverse events will be provided for each of the three Safety Populations that summarizes incidence in the following categories, overall, by age group (pediatric, adult), and by sex:

- Any AEs
- Any TEAEs
- TEAEs by relationship to study medication (Not related, Unlikely Related, Possibly Related or Related)
- TEAEs by severity (mild, moderate, severe)

- Any TEAEs with an outcome of death
- TESAEs
- Treatment discontinuation due to TEAEs

The incidence of TEAEs will be summarized for each treatment group by Preferred Term as well as by Preferred Term within System Organ Class. The incidence of TEAEs by severity and relationship to treatment will be summarized for each treatment group by System Organ Class and Preferred Term. A patient with several occurrences of the same AE will be counted once and classified by the most severe event (or the event with the closest relationship to study drug). If severity or causality is missing, the worst case will be assumed (i.e., “Severe” if severity is missing and “Drug Related” if causality is missing.)

In addition, the incidence of Adverse Events of Interest (AEOIs), TESAEs, TEAEs leading to treatment discontinuation, and TEAEs leading to death will be summarized for each treatment group by System Organ Class and Preferred Term.

Incidence calculations will be based on the numbers and percentages of patients with AEs, and sorted by decreasing frequency in the fosmetpantotenate group. Although a MedDRA Preferred Term may be reported more than once for a patient, that patient will be counted only once for that MedDRA Preferred Term. For these summaries, patients with multiple AEs will be counted only once per SOC and PT. Furthermore, for each category within these summaries, the number of adverse events will be presented.

The above incidence tables will each be run using the Double-Blind, Open-Label, and Fosmetpantotenate Safety Populations.

In addition, time to event analyses (first event) will be performed for the following adverse event categories for patients in the Double-Blind Safety Population: dystonia, any AE with gastrointestinal disorder as SOC, any AEOI. Time to event endpoints will be summarized using the Kaplan-Meier method; median event times and 2-sided 95% confidence interval for each median will be provided (Brookmeyer, 1982). Time to event data will be censored using the date of a patient’s last visit during the double-blind period. The event or censoring time (days) will be calculated as:

$$\text{Date of event/censoring} - \text{Date of randomization} + I$$

Moreover, for each AE category, a log-rank test will be performed to compare time to event between the treatment groups. The Cox proportional hazard (PH) model will be fitted and the estimated hazard ratio and 2-sided 95% confidence interval will be provided. Finally, estimates of the time to event curves obtained from the Kaplan-Meier method will be presented and displayed graphically, spanning the double-blind period.

For the above three adverse event categories, the duration of each event within the event category will be summarized descriptively, for each event occurrence, for patients in the

Double-Blind Safety Population. In addition, patient-level duration of events will be displayed graphically using the MedDRA Preferred Term, spanning the double-blind period. Only patients who have had an adverse event in the given adverse event category will be presented, and multiple occurrences of a single Preferred Term will be presented on the same line.

By-patient listings of deaths, TESAEs, AEs leading to treatment discontinuation, AEOIs, as well as all AEs will be provided. The by-patient AE data listings will include age group, onset and resolution dates, study period, verbatim term, System Organ Class, Preferred Term, period, severity, seriousness criteria, relationship to treatment, action taken for the event, other action, and outcome. The listings will include all data observed across the double-blind and open-label periods, using the Double-Blind Safety Population.

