Patients who permanently discontinue study medication early should be encouraged to continue study visits through Week 120 for continued collection of safety and efficacy data despite stopping study medication, but may withdraw consent at any time (see [Section 6.3.3](#)). Patients who agree to continue regularly scheduled study visits will complete the End of Treatment assessments listed in the schedule of events ([Section 15.1](#)) as close as possible to the patient's last dose of study medication. The visit data, including the primary reason for discontinuation of study medication, will be recorded on the End of Treatment eCRF. Subsequent study visit data will be recorded on the visit-specific eCRF, and the patient's final study visit will be recorded on the End of Treatment/Early Termination eCRF.

For patients who permanently discontinue study medication, the Investigator should resume standard of care treatment, including treatment with appropriate medications, as deemed necessary.

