10.5. Reporting Adverse and Serious Adverse Events

10.5.1. Reporting Adverse Events

AEs will be captured from the time the main study informed consent is signed to 30 days after the patient's last dose of investigational product or the patient's last scheduled visit, whichever occurs last.

- AEs should be recorded using appropriate medical terminology. When recording, it is preferable to provide a diagnosis. In the absence of a diagnosis, each sign and symptom should be captured as a unique AE. Sufficient information should be sought to assist the Investigator both in determining the diagnosis and in making a causality assessment.
- Reporting should not be delayed pending receipt of all required information. If information is unavailable at the time of the initial report, the Investigator is expected to follow-up until the required information has been obtained or until 30 days after the patient's last dose or last scheduled visit.

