12.7.3. Adverse Events

All AEs will be coded by Preferred Term and System Organ Class using the most recent version of MedDRA available at study initiation. By-patient listings of deaths, SAEs, and AEs leading to treatment discontinuation will be provided. The by-patient AE data listings will include onset and resolution dates, verbatim term, System Organ Class, Preferred Term, treatment, severity, relationship to treatment, action taken for the event, and outcome.

TEAEs in the double-blind period are defined as AEs that are new or are a worsening of an existing condition that begins from the day of first dose of investigational product until the day after the last dose for the double-blind treatment period. The incidence of TEAEs will be summarized for each treatment group by Preferred Term within body system, overall and by severity and relationship to treatment. Incidence calculations will be based on the numbers and percentages of patients with AEs. Although a MedDRA term may be reported more than once for a patient, that patient will be counted only once for that MedDRA term.

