Abbreviations: BAD = Barry Albright Dystonia; CGI-I = Clinician Global Impression of Improvement; Con meds = concomitant medications; C-SSRS = Columbia Suicide Severity Rating Scale; D = Day; EQ-5D-3L/EQ-5D-Y = EuroQol 5-dimension, 3-level quality of life instrument/EuroQol-5D Youth Version; FIM/WeeFIM = Functional Independence Measure/Functional Independence Measure for Children; IRB/IEC = Institutional Review Board/Independent Ethics Committee; Neuro-QoL = quality of life measure for adults/children with neurological disorders; PK = pharmacokinetic; PKAN-ADL = Pantothenate Kinase-associated Neurodegeneration Activities of Daily Living; Unshed = unscheduled; UPDRS = Unified Parkinson's Disease Rating Scale; V = Visit; W = Week

- ¹ For patients who are taking deferiprone or who require confirmation of mutation in the *PANK2* gene. This visit will be accomplished at least 30 days prior to the Screening visit for washout of deferiprone.
- ² Patients who fail screening for any reason may be re-screened up to 2 times. Re-screening will consist of confirmation of inclusion and exclusion criteria, for re-screening criteria, refer to the [Section 6.2](#) and [Section 9.2](#).
- ³ If a patient requires an unscheduled visit, assessments related to the purpose of the visit should be performed (see [Section 9.7](#)).
- ⁴ For patients who are prematurely withdrawn from treatment (End of Treatment) or from the study (Early Termination) during the double-blind period. Patients who agree to continue regularly scheduled study visits will complete the End of Treatment as close as possible to the patient's last dose of study medication. In addition to the Early Termination Visit, patients who prematurely discontinue from the study will be contacted (via telephone call) 30 days (± 7 days) after the last dose of investigational product to ascertain patient safety. If a patient who has prematurely discontinued study medication, decides to withdraw consent/assent and discontinue from the study within 6 weeks of completing the End of Treatment, the End of Treatment Visit conducted at the time of study medication withdrawal may serve as the patient's final site visit.
- ⁵ Includes the PKAN-specific Medical History Form.
- ⁶ The C-SSRS will be completed in patients who are determined by the Investigator to be assessable. See [Section 9.3.5](#) for definition of assessable patients and assessments.

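### The double-blind TEAE window closes one day after the last blinded dose, so new serious or fatal events after early stopping fall outside the placebo-controlled TEAE, TESAE and TEAE-death tables

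*SAP*

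**What the plan says.** **Window for counting.** Protocol 12.7.3 defines a double-blind TEAE as a new or worsened condition that "begins from the day of first dose of investigational product until the day after the last dose for the double-blind treatment period". SAP 4.11.1 repeats the rule: onset counts from the first dose "until the day after the last dose for the double-blind treatment period".

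**Window for collecting.** Protocol 10.5.1 captures AEs up to "30 days after the patient's last dose of investigational product or the patient's last scheduled visit, whichever occurs last". Under Protocol 6.5.4.2, patients who stop drug for good "should be encouraged to continue study visits through Week 120 for continued collection of safety and efficacy data". Under the footnotes to Table 15.1-1, patients who leave the study during the double-blind period are telephoned about 30 days "after the last dose of investigational product to ascertain patient safety".

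**Other windows in SAP 4.11.1.** Open-label TEAEs are those that "begin from the day of first dose of open-label investigational product", with no end stated. The window for the Fosmetpantotenate Safety Population also has a start and no end. For the comparisons of time to first dystonia, gastrointestinal or AEOI event, "Time to event data will be censored using the date of a" patient's last double-blind visit.

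**What is tabulated.** In SAP 4.11.1 the summaries by System Organ Class and Preferred Term, severity and relationship, and those for serious events, discontinuation and death, are restricted to treatment-emergent events. The overview also has a row for any AE, separate from any TEAE. AEOI incidence carries no treatment-emergent qualifier. Listings cover all AEs, deaths and AEOIs.

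**The concern.** The trial goes on collecting safety data after a patient stops blinded drug, but its main by-arm safety tables stop counting the next day. An SAE that starts a week after stopping is recorded with its date and still does not reach the by-arm TESAE table. A clinically significant laboratory abnormality first found at the End of Treatment visit can be dated outside the window if that visit falls more than a day after the last dose.

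The double-blind period is the only randomised comparison. If stopping differs between arms, a rule that drops events after stopping removes different amounts of follow-up from each arm. There is also an asymmetry between populations. A late SAE in an active-arm stopper is treatment-emergent in the Fosmetpantotenate Safety Population, which has no comparator. The same event in a placebo stopper who never takes open-label drug is treatment-emergent in no population.

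**Working it through.** **1. Where a late event goes.** Take a patient who stops blinded drug early, takes no open-label dose, and has a new SAE starting on day 2 or later after the last dose.

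| Output | Active arm | Placebo arm |
|---|---|---|
| Double-blind TEAE tables by SOC/PT, severity, relationship | not counted | not counted |
| Double-blind TESAE and TEAE-death tables | not counted | not counted |
| Open-Label Safety Population | not a member | not a member |
| Fosmetpantotenate Safety Population TEAE tables | counted | not a member |
| Double-blind any-AE overview row | counted if within the double-blind period | same |
| AEOI incidence; dystonia, GI and AEOI time to event | possibly | possibly |
| All-AE listing; death and AEOI listings where they apply | listed | listed |

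The word *possibly* depends on event type and on where the double-blind period ends for an early stopper. SAP 4.11 limits Double-Blind Safety Population tables to data from that period but does not define its end for such patients.

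**2. The plan's own figure.** SAP 4.2 assumes a difference of 3, SD 4.5, two-sided alpha 0.05 and 37 per arm. The noncentral t calculation gives 80.8% power, in line with the stated 80%. Allowing for 10% attrition, 74 / 0.90 = 82.2, against 82 stated. This point does not affect those figures. They supply only a planning number of non-completers: 82 − 74 = 8 (9.8%).

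**3. Minimum gap.** Collection runs to at least last dose + 30 days and counting to last dose + 1.
- Per stopper: 30 − 1 = 29 days.
- Over 8 stoppers: 8 × 29 = 232 patient-days.
- Planned double-blind follow-up: 82 × 168 = 13,776 patient-days.
- Share: 232 / 13,776 = 1.7%.

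**4. Gap for patients followed off drug to Week 24.** With the last dose at Week w, the uncounted days are 168 − (7w + 1).

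| Stop at Week | Uncounted days |
|---|---|
| 3 | 146 |
| 6 | 125 |
| 12 | 83 |
| 18 | 41 |

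**5. How many SAEs this could be.** The documents give no rate, so the 30-day risk r of a new SAE after stopping is an assumption, shown over a range. The risk over the 29 excluded days is p = 1 − (1 − r)^(29/30). The expected number of patients left out of 8 is 8p, and the chance of at least one is 1 − (1 − p)^8.

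| Assumed r | Expected patients omitted | Chance of at least one |
|---|---|---|
| 2% | 0.15 | 14% |
| 5% | 0.39 | 33% |
| 10% | 0.77 | 56% |
| 20% | 1.55 | 82% |

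These counts cover both arms together. With 82 / 2 = 41 patients per arm, one SAE is 1 / 41 = 2.4% of an arm.

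**The case against.** The case for leaving the rule alone is reasonable. Protocol and SAP agree on the window, so it is a prespecified on-treatment definition and not a slip. It needs an end because another treatment period follows. After stopping, standard care resumes in a progressive disease, so later events mix drug effect, disease and other therapy. The rule works on onset: an event that caused stopping normally began on drug and is kept, and a fatal event with on-treatment onset stays in the death table whenever death occurs. Completers who move directly to open label are largely unaffected. All of this stands, and it supports keeping the on-treatment table.

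A reader might go further and infer that these events vanish from every placebo-controlled output. The documents do not support that. The any-AE row is by arm, the AEOI incidence as worded is not tied to the window, the three time-to-event comparisons run to the last double-blind visit, and the listings show seriousness and onset date. None of the by-arm outputs, however, tabulates SAEs or deaths as such after an early stop.

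A reader might also infer that harm is concentrated among early stoppers, or that one arm is favoured. The documents give no event rate and no stopping rate by arm, so neither can be claimed.

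The figure of 8 is a fair target too. SAP 4.2 plans for attrition from the double-blind period, and patients who stop drug but attend to Week 24 may not count as attrition.

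**Conclusion.** The concern holds in a limited form. New SAEs and fatal AEs that start two or more days after an early stop are collected but left out of the placebo-controlled TEAE, TESAE and TEAE-death tables. For placebo patients who never take open-label drug, they are treatment-emergent in no population.

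The gap is at least 29 days per early stopper. If the 8 planned non-completers stand in for early stoppers, that is 232 patient-days, or 1.7% of planned follow-up. It is longer for anyone followed off drug, up to 146 days for a stop at Week 3. The number of SAEs affected rests wholly on an assumed risk: 0.15 to 1.55 patients in total for a 30-day risk of 2% to 20%. No arm imbalance or changed safety conclusion has been shown. The change is still worth making, because the data are already collected and a single SAE is visible in arms of about 41.

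**What to change.** In SAP 4.11.1, with a matching sentence in Protocol 12.7.3:

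1. Add by-arm incidence tables of all AEs, SAEs and deaths for the Double-Blind Safety Population. Run them from first blinded dose to the later of last blinded dose + 30 days or the last double-blind visit, and cut every patient at the first open-label dose. The cut also deals with patients who start open label after a gap.
2. Keep the present version, ending one day after the last dose, and label it on-treatment.
3. Define the end of the double-blind period for early stoppers in the same terms, so that the any-AE row and the AEOI tables have a clear reach.
4. Leave time-to-event censoring no earlier than the last double-blind visit. Censoring at last dose + 30 days would shorten it: a patient who stops at Week 3 and attends to Week 24 would be censored near Day 21 + 30 = 51 instead of near Day 168.

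The cost is a few sentences and a rerun of existing tables, with no new data collection. A few off-drug, disease-related events will enter the added tables in both arms; showing the on-treatment version beside them lets a reader judge their weight.
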